8.1.2. Summary Measure

The following PK parameters will be derived and summarized as data permits:

- Part 1 (single dose): $AUC_{(0-24)}$, $AUC_{(0-t)}$, $AUC_{(0-inf)}$, C_{max} , C_{24} , t_{max} , t_{lag} , $t_{1/2}$, C_{last} , t_{last} , CL/F
- Part 2 (repeated once daily [QD] dose):
 - Day 1: $AUC_{(0-24)}$, C_{max} , C_{24} , t_{max} , t_{lag}
 - Day 14 (Cohorts 3 and 4): $AUC_{(0-t)}$, C_{max} , $C\tau$, t_{max} , $t_{1/2}$, and CL/F
 - Day 14 (Cohort 5): $AUC_{(0-t)}$, C_{max} , $C\tau$, t_{max}
 - Day 18 (Cohort 5): $AUC_{(0-t)}$, C_{max} , $C\tau$, t_{max} , $t_{1/2}$, and CL/F
- Part 2 (repeated once weekly [QW] dose, as data permits):
 - Day 1 (Cohort 6): $AUC_{(0-168)}$, C_{max} , C_{168} , t_{max} , t_{lag}
 - Day 8 (Cohort 6): $AUC_{(0-168)}$, C_{max} , C_{168} , t_{max}
 - Day 15 (Cohort 6): $AUC_{(0-t)}$, C_{max} , $C\tau$, t_{max} , $t_{1/2}$, and CL/F
- Part 3 (single dose): $AUC_{(0-24)}$, $AUC_{(0-inf)}$, C_{max} , C_{24} , t_{max} , t_{lag} , $t_{1/2}$, C_{last} , t_{last} , CL/F

Additionally, in Part 3 the parameters used for the treatment comparison of relative bioavailability of the single dose PiB formulation relative to the single dose tablet formulation, and the food effect of the tablet fed relative to tablet fasted state will be $AUC_{(0-24)}$, $AUC_{(0-inf)}$, and C_{max} .

8.1.3. Population of Interest

The primary pharmacokinetic analyses will be based on the Pharmacokinetic population, unless otherwise specified.

8.1.4. Strategy for Intercurrent (Post-Randomization) Events

Missing data will not be imputed, regardless of the reason.

8.1.5. Statistical Analyses / Methods

Details of the planned displays are provided in [Appendix 10](#) and will be based on GSK Data Standards and statistical principles.

Unless otherwise specified, endpoints/variables defined in Section [8.1.1](#) will be summarised using descriptive statistics, graphically presented (where appropriate) and listed.

8.1.5.1. Statistical Methodology Specification

The following pharmacokinetic statistical analyses will only be performed if sufficient data is available (i.e. if participants have well defined plasma profiles).

8.1.5.1.1. Dose Proportionality (Power Model)

Part 1 and 2

In Part 1 where participants may participate in multiple cohorts the power model will be used to estimate the dose proportionality constant as follows:

$$y_{ij} = \theta_1 + \theta_2 d_{ij} + s_i + \epsilon_{ij}$$

Where y_{ij} is log-PK of i -th participant to j -th dose, d_{ij} is j -th log-dose administered to i -th participant. θ_1 and θ_2 are population intercept and slope, respectively, s_i is random effect of i -th participant and ϵ_{ij} is random error of i -th participant in j -th dose.

The posterior distribution of the mean value μ_{ij} of the log-PK parameter is then described as:

$$\mu_{ij} \sim N(y_{ij}, \sigma^2)$$

In Part 2 where participants will only participate in one cohort and intra-participant variability cannot be estimated the following power model will be used to estimate the dose proportionality constant.

$$y_i = \theta_1 + \theta_2 d_i + \epsilon_i$$

[2]

Where y_i is log-PK of i -th participant, d_i is the log-dose administered to i -th participant. θ_1 and θ_2 are population intercept and slope respectively and ε_i is random error of i -th participant.

The posterior distribution of the mean value μ_i of the log-PK parameter is then described as:

$$\mu_i \sim N(y_i, \sigma^2)$$

In both models θ_2 represents the dose proportionality constant. The point estimate and 95% credible interval for this parameter will be estimated and reported using separate models for Part 1 and Part 2.

Non-informative prior distributions for the estimated parameters are defined below:

$$\theta_1 \sim N(0, 10^2)$$

$$\theta_2 \sim N(0, 10^2)$$

$$s_i \sim N(0, \tau_i)$$

$$\tau_i \sim Gamma(0.01, 0.01)$$

$$\sigma^2 \sim Gamma(0.01, 0.01)$$

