Dosing	
Part 1 (SAD):
 
 • In Part 1 participants will receive a single dose of VH3739937 • Dose escalation in Part 1 will be determined by the Dose Escalation Committee based on the double-blind (sponsor-unblinded) safety data and the PK data from the current and previous dose(s). • Dose escalation will not exceed approximately 3-fold between doses up to approximately the predicted minimally effective dose and will not exceed 2-fold thereafter. • Dose escalation in Part 1 will require (from the current dosing group) at least 24 hours of safety and PK data from 4 participants receiving active drug. Dose escalation will be guided by safety and the SAD PK stopping criteria (see Protocol Section 8). • Due to the alternating dosing periods between Cohort 1 and Cohort 2, a participant in either cohort will receive the next dose after approximately 3 or 4 weeks. 
Part 2 (MAD):
 
 • In Part 2 participants will receive a single dose of VH3739937 each day for either 14 days (Cohorts 3 and 4) 18 days (Cohort 5), or once weekly for 3 weeks (Cohort 6) • Part 2 (MAD) of the study will be initiated once the single dose safety and preliminary PK data for the anticipated minimally effective dose has been evaluated in the SAD. • The potential minimally effective dose for VH3739937, noted as 25 mg, is anticipated to be that which is predicted to provide a steady state C_{trough} \geq 0.258 μg/mL in 95% of participants and will be re-estimated based on the PK data collected in the early doses in Part 1. • Dose escalation in Part 2 will be determined by the VH/GSK study team and the PI based on the double-blind (sponsor-unblinded) safety and PK data (minimally up to 24 h post Day 14 dose) from the current and previous dosing cohort(s). Specifically, 14 days of safety and PK data (minimally up to 24 h post Day 14 dose) from a minimum of five participants in current cohort receiving active drug will be required for dose escalation

Overview of Study Design and Key Features																																	

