Treatment Assignment	
Part 1 (SAD):
 
 Participants in either Cohort 1 or Cohort 2 will be assigned to 1 of the 3 treatment sequences in a cross-over, and each participant will receive placebo once. 
  
 Cohort 1	Period 1	Period 2	Period 3	
   
 Sequence 1	Placebo	Dose 3	Dose 5	
 
 Sequence 2	Dose 1	Placebo	Dose 5	
 
 Sequence 3	Dose 1	Dose 3	Placebo	
  
 
  
 Cohort 2	Period 1	Period 2	Period 3	
   
 Sequence 1	Placebo	Dose 4	Dose 6	
 
 Sequence 2	Dose 2	Placebo	Dose 6	
 
 Sequence 3	Dose 2	Dose 4	Placebo	
  
 
 When the 800 mg dose is evaluated, 9 new participants, who were not previously exposed to any dose of VH3739937 will be enrolled in the study. Six participants randomized to receive VH3739937 and 3 participants will be randomized to receive placebo. 
Part 2 (MAD):
 
 In Cohorts 3 to 5, 10 participants per cohort (active/PBO=7/3) will receive a once-daily dose of VH3739937 or PBO for 14 days (Cohort 3 and 4) or 18 days (Cohort 5) In Cohort 6, 10 participants (active/PBO=7/3) will receive a once-weekly dose of 500 mg VH3739937 or PBO over the course of 14 days (Doses on Day 1, 8, and 15) 	Cohort 1	Period 1	Period 2	Period 3	Sequence 1	Placebo	Dose 3	Dose 5	Sequence 2	Dose 1	Placebo	Dose 5	Sequence 3	Dose 1	Dose 3	Placebo	Cohort 2	Period 1	Period 2	Period 3	Sequence 1	Placebo	Dose 4	Dose 6	Sequence 2	Dose 2	Placebo	Dose 6	Sequence 3	Dose 2	Dose 4	Placebo
Cohort 1	Period 1	Period 2	Period 3																														
Sequence 1	Placebo	Dose 3	Dose 5																														
Sequence 2	Dose 1	Placebo	Dose 5																														
Sequence 3	Dose 1	Dose 3	Placebo																														
Cohort 2	Period 1	Period 2	Period 3																														
Sequence 1	Placebo	Dose 4	Dose 6																														
Sequence 2	Dose 2	Placebo	Dose 6																														
Sequence 3	Dose 2	Dose 4	Placebo																														

Overview of Study Design and Key Features	

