8.1.5.1.2. Accumulation Ratio

Part 1

Predidicted daily dose accumulation from single dose data (Part 1) for AUC will be as follows:

$$Rp(AUC) = \frac{AUC(0 - \infty)}{AUC(0 - 24)}$$

Point estimates of the mean ratio and associated 90% confidence intervals will be displayed by treatment.

Part 2

Accumulation will also be evaluated for each treatment by determining the ratio of Day 14 (Part 2 cohort 3 and 4) or Day 18 (Part 2 cohort 5) to Day 1 AUC(0- τ) (R(AUC(0- τ)), Cmax (R(Cmax)), and C τ (R(C τ)). Day 1 C τ will be defined as the 24-hr post day 1 dosing concentration (C24 for Day 1). For part 2 cohort 3,4, and 5 the dosing interval is 24-hrs. Therefore, $\tau=24$ hrs.

For Cohort 6 accumulation will be evaluated by determining the ratio of third dose (occurring on Day 15) to first dose (Day 1) for AUC(0- τ) (R(AUC(0- τ)), Cmax

(R(Cmax)), and C τ (R(C τ)). For part 2 cohort 6 the dosing interval is 7 days (168 hrs). Therefore, $\tau=168$ hrs. In Cohort 6, since sampling at 168 hrs post 3rd dose was not collected, it will be predicted using linear model based on the other collected timepoints post dose.

Point estimates of the mean ratios and associated 90% confidence intervals will be displayed by treatment.

Endpoint / Variables

 • Rp(AUC) for Part 1 Where $Rp(AUC) = \frac{AUC(0 - \infty)}{AUC(0 - 24)}$ • R(AUC(0-τ)), R(Cmax), R(Cτ) on Days 1 and 14 for Part 2 Cohort 3 and 4 where, $\tau=24$ hrs • R(AUC(0-τ)), R(Cmax), R(Cτ) on Days 1 and 18 for Part 2 Cohort 5 where, $\tau=24$ hrs • R(AUC(0-τ)), R(Cmax), R(Cτ) on Days 1 and 15 for Part 2 Cohort 6 where, $\tau=168$ hrs 
Where
 $R(Parameter) = \frac{(Parameter\ Value\ on\ Day\ XX)}{(Parameter\ Value\ on\ Day\ 1)}$
Model Specification

 • In Part 1 the mean of the raw mean of the ratio of AUC(0-inf) to AUC(0-24) will be reported. There is no formal modeling. • In the model for Part 2 Cohort 3,4,5,6 the ratio of the specific parameter will be the dependent variable, day will be included as a fixed effect categorical variable with the reference as Day 1, and participant will be included as a random effect.
Model Checking & Diagnostics

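### Read as written, the SAP's Part 2 power model pools the weekly 500 mg cohort with the daily cohorts, so the Cmax slope (and the Ctau slope, if fitted) would reflect the dosing interval and not dose proportionality.

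*SAP*

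**What the plan says.** SAP 8.1.5.1.1 sets out two power models. Part 1 has a participant random effect. For Part 2 the text reads "In Part 2 where participants will only participate in one cohort and intra-participant variability cannot be estimated the following power model will be used", and in that model "d_i is the log-dose administered to i -th participant". There is no term for regimen or dosing interval. The slope and its 95% credible interval "will be estimated and reported using separate models for Part 1 and Part 2", and no cohort is named.

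Part 2 is not one regimen. Cohorts 3, 4 and 5 are dosed daily. SAP 2.3 adds: "In Cohort 6, 10 participants (active/PBO=7/3) will receive a once-weekly dose of 500 mg VH3739937 or PBO over the course of 14 days". SAP 8.1.5.1.2 gives the interval as 24 h for Cohorts 3 to 5 and 168 h for Cohort 6.

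The Part 2 dose-proportionality endpoints in SAP 2.2 are AUC(0-tau), Cmax and Ctau, with no cohort limit. The planned display, Table 4.5 in SAP 13.10.6, lists AUC(0-inf), AUC(0-tau) and Cmax. It omits Ctau and names no cohorts. Protocol 9.4.4 says only that selected single- and repeated-dose parameters go into the power model.

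Neighbouring sections do name cohorts. The accumulation section handles Cohort 6 separately, the steady-state section covers Cohorts 3 to 5 only, and the notes to Table 4.6 refer to daily dosing.

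**The concern.** A power-model slope measures dose proportionality only if dose is the one thing that differs systematically between groups. With a half-life of about 90 h, daily dosing accumulates roughly 6-fold and weekly dosing only about 1.3-fold. Peak and trough per milligram are therefore much lower on the weekly schedule, whatever the drug's linearity. Because the weekly cohort also has the highest dose, it has high leverage and pulls the fitted line down.

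Dose proportionality after repeated dosing is a secondary objective. A programmer who follows the text as it stands could report a narrow interval well below 1 for a drug that is perfectly dose-proportional. If the cohorts are chosen after the results are seen, the choice is data-driven.

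**Working it through.** **Inputs.** Median projections from protocol Table 11 (section 4.3.7), in µg/mL, for 50 mg daily, 100 mg daily and 500 mg weekly: Cmax 0.968, 1.72, 1.5; Ctau 0.905, 1.57, 0.429. Half-life about 90 h (protocol 4.1). Seven active participants per cohort (SAP 2.3). Between-participant CV of 25, 35 and 50% (the AUC range in protocol 9.5, assumed here to apply to Cmax and Ctau as well). Table 11 has no 25 mg column.

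**The plan's own figure first.** Accumulation is R = 1/(1 - 2^(-tau/90)). Daily: 1/(1 - 2^(-24/90)) = 5.93, which reproduces the stated 6-fold. Weekly: 1/(1 - 2^(-168/90)) = 1.38, or 1.35 after three doses, close to the stated 1.3.

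**Slopes from Table 11.** These are least-squares fits of log(parameter) on log(dose), which is what the Part 2 model gives with its vague priors.

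- 50 and 100 mg daily only: Cmax ln(1.72/0.968)/ln 2 = 0.83; Ctau ln(1.57/0.905)/ln 2 = 0.79.
- Adding 500 mg weekly: Cmax 0.14; Ctau -0.41.
- Adding an extrapolated 25 mg value as well (assumed slope 0.8 to 1.0 between 25 and 50 mg): pooled Cmax 0.31 to 0.35; pooled Ctau -0.11 to -0.07.

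**Exactly proportional drug (true slope 1).** With n doses, R_n = (1 - 2^(-n·tau/90))/(1 - 2^(-tau/90)). For 14, 14 and 18 daily doses and 3 weekly doses, R_n = 5.480, 5.480, 5.713 and 1.349. Cmax is proportional to dose × R_n, Ctau to that × 2^(-tau/90), and AUC(0-tau) to dose × R_n × (1 - 2^(-tau/90)).

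| Relative value | 25 mg daily | 50 mg daily | 100 mg daily | 500 mg weekly | Daily slope | Pooled slope |
|---|---|---|---|---|---|---|
| Cmax | 137.0 | 274.0 | 571.3 | 674.7 | 1.03 | 0.51 |
| Ctau | 113.9 | 227.8 | 474.9 | 185.0 | 1.03 | 0.12 |
| AUC(0-tau) | 23.1 | 46.2 | 96.4 | 489.7 | 1.03 | 1.02 |

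The daily slope is 1.03 and not 1.00 because Cohort 5 is taken on Day 18 (96.4% of steady state) and Cohorts 3 and 4 on Day 14 (92.5%). Mixing the days therefore adds about 0.03.

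**Certainty of the wrong answer.** In 2,000 simulated data sets per setting (Table 11 medians, 25 mg extrapolated at the 50 to 100 mg slope), every pooled 95% interval for Cmax and Ctau excluded 1 at all three CVs. At CV 25% the mean pooled interval was 0.18 to 0.45 for Cmax and -0.30 to 0.09 for Ctau. With daily cohorts only it was 0.64 to 1.03 and 0.60 to 0.99.

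**Precision lost by leaving Cohort 6 out.** The 95% half-width is t × s/√Sxx, where s = √ln(1 + 0.25²) = 0.246 at CV 25%. Daily cohorts: Sxx = 7 × 2 × (ln 2)² = 6.73, t(19) = 2.09, half-width 0.20. All four cohorts: Sxx = 34.6, t(26) = 2.06, half-width 0.09.

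**The case against.** The strongest reply is that the SAP never says Cohort 6 is in the model. It separates daily from weekly in the treatment codes, the parameter lists and the accumulation section. The Table 4.5 shell, which might name cohorts, is available only on request. This stands in part: pooling follows from silence, and a reader who infers that the SAP expressly plans it goes further than the text. But silence next to sections that do name cohorts is not an exclusion, and the literal reading gives a wrong Cmax slope.

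Second, Ctau has the most striking figures but is missing from Table 4.5. That also stands, so the point must rest on Cmax, which is in both the endpoint list and the display.

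Third, a reader might infer that every Part 2 slope is spoiled. The documents do not support that for AUC(0-tau). Table 11 cannot settle it: its 500 mg AUC is a 24-hour value, so a fit to those medians (0.81 falling to 0.27) does not describe AUC(0-tau). The linear calculation does, and it gives 1.02. For the same reason, it would be wrong to say that dropping Cohort 6 costs nothing: for AUC(0-tau) it carries real information.

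Fourth, the analysis is secondary, estimates only, and has no acceptance range attached to the slope. This limits the consequence but does not make the estimate right.

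**Conclusion.** The concern holds for Cmax, and for Ctau if it is analysed. Run as written, the Part 2 model would report a slope driven by the dosing interval: 0.14 for Cmax against 0.83 on the Table 11 medians, or 0.51 for a drug whose true slope is 1. It does not hold for AUC(0-tau) under approximately linear kinetics.

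The choice of Cohort 5 day is a minor matter. A reader might take mixing Day 14 and Day 18 as a serious bias, but 0.03 is small beside a half-width of about 0.20, and protocol section 3 itself lists Day 14 for Cohorts 3 and 4 and Day 18 for Cohort 5.

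These sizes assume that Table 11 medians stand in for the data, that the half-life is 90 h with one-compartment superposition, and that any 25 mg value is extrapolated as stated. The direction does not depend on the extrapolation, because the three tabulated doses alone show it.

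**What to change.** - In SAP 8.1.5.1.1 and the notes to Table 4.5, state that the Part 2 power model for Cmax and Ctau uses daily Cohorts 3, 4 and 5 only, and that Cohort 6 Cmax and Ctau are summarised descriptively. One weekly dose level cannot give a weekly slope.
- For AUC(0-tau), make the daily cohorts the main fit. A fit that adds Cohort 6 with AUC(0-168) may be reported as supportive.
- Either add Ctau to Table 4.5 or remove it from the Part 2 dose-proportionality endpoints in SAP 2.2.
- State which Cohort 5 day enters the model. Day 14 and Day 18 parameters are both already derived (SAP 8.1.2).

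The cost is a few sentences and no new data. The statistical price is precision for AUC(0-tau): at CV 25% with 7 active per cohort, the daily-only 95% half-width is about 0.20 against 0.09 with Cohort 6 included. The supportive fit recovers this if linearity holds. If it uses the third weekly dose, it needs a 168 h concentration that is not sampled. SAP 8.1.5.1.2 predicts that value from a linear model, while the Table 4.8 note substitutes the 192 h sample, so one rule should be stated.

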The SAD portion of the study will be conducted in an interlocking fashion with two separate cohorts each of approximately 9 healthy participants. Each of these two cohorts may contain a minimum of three escalating doses of VH3739937 through to 640 mg. An additional 800 mg dose will be evaluated as this was indicated following review of safety and PK data from participants dosed up to 640 mg. The interlocking design shown in [Figure 3](#) and the randomization sequence in [Table 7](#) will allow the 9 participants in each cohort to potentially receive one of the lower and one of the higher doses of VH3739937. Participants in Cohort 1 and Cohort 2 will follow the same randomization strategy with alternating ascending doses ([Table 7](#)). In each escalating dose period, 6 participants will be randomized to receive VH3739937 and 3 participants will be randomized to receive placebo. Participants in either Cohort will be assigned to one of the three treatment sequences, and each participant will receive placebo at least once. When the 800 mg dose is evaluated, 6 participants from both Cohorts 1 and 2 will be randomized to receive VH3739937 and 3 participants will be randomized to receive placebo, independent of which prior doses they received.

Details of the starting dose and dose escalation can be found in Section 4.3

Table 7 Description of treatment sequences in Cohort 1 and Cohort 2 Periods 1, 2, and 3

Cohort 1	Period 1	Period 2	Period 3
Sequence 1	Placebo	Dose 3	Dose 5
Sequence 2	Dose 1	Placebo	Dose 5
Sequence 3	Dose 1	Dose 3	Placebo

Cohort 2	Period 1	Period 2	Period 3
Sequence 1	Placebo	Dose 4	Dose 6
Sequence 2	Dose 2	Placebo	Dose 6
Sequence 3	Dose 2	Dose 4	Placebo

For Part 1, 24-hour continuous Holter/ ECG recordings will be collected on the day before dosing (Day -1), and Day 1 for extraction of ECGs paired with PK sampling.

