4.3.2. Predicted Human Effective Dose

Trough concentrations (C_t) are typically the PK parameter of interest for efficacy for other antiretroviral classes such as protease inhibitors and integrase inhibitors. The target C_t for VH3739937 was established using the average of 3-times the protein binding-adjusted EC₉₀ (3xPBA-EC₉₀) for a small library of 6 Gag/Pr genotyped viruses less sensitive to a precursor maturation inhibitor GSK3640254. These viruses exhibited an average 3xPBA-EC₉₀ of 312 nM (0.258 μ g/mL). A similar 3xPBA-EC₉₀ value was observed towards Δ 370 virus (309 nM). The predicted dose that achieves a C_t at steady-state \geq target concentration in \sim 95% of the simulated subjects will be selected as the minimal effective dose.

Prior to study initiation, the rationale for estimation of the minimally effective dose and associated PK parameters was as follows:

The potential minimal effective dose for VH3739937 was estimated using the predicted human PK profile, assuming 50% between subject variability (IIV) on CL, V₂ and K_a, the same parameters for which moderate to high IIV was estimated in a preliminary population PK model for GSK3640254, based on data from a FTIH study profile [GlaxoSmithKline Document Number [2020N427033_00](#)]. This led to the prediction of a likely minimally effective once daily dose of approximately 80 mg. At this dose, the mean repeat-dose C_{max} is predicted to be approximately 0.94 μ g/mL, mean C_t is predicted to be approximately 0.68 μ g/mL and mean AUC is predicted to be approximately 20.1 μ g*h/mL ([Table 10](#)). The anticipated steady-state mean AUC is 1.27-fold lower than the no observed adverse effect level (NOAEL) in the rat (25.5 μ g*h/mL), 4.79-fold lower than the lowest observed adverse effect level (LOAEL) in the rat (96.2 μ g*h/mL), and 2.58-fold lower than the LOAEL in the dog (51.9 μ g*h/mL).

However, during the course of study 212548 conduct, modelling and simulation of PK data from SAD treatment Periods 10 mg, 30 mg, 80 mg, 160 mg, 320 mg and 640 mg have led to the revision of the estimation of the predicted minimally effective dose and associated PK parameters. More detailed information may be found in the IB Supplement [GlaxoSmithKline Document Number [2021 RPS_CLIN_004025](#)].

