3. PLANNED ANALYSES

3.1. Interim Analyses

There will be no formal interim analysis; however, all preliminary safety, tolerability, and available pharmacokinetic data will be reviewed internally at the Dose Escalation Committee (ViiV/GSK) prior to each dose escalation or administration and according to the dose escalation charter. Safety data (labs, vital signs, ECG, AEs, SAEs) will be reviewed by the PI/Sub-I and ViiV/GSK study team after completion of each dose level. Dose escalation can only occur after PI/Sub-I and ViiV/GSK study team has found that the safety, PK profiles are supportive to proceed with the evaluation of the next highest dose level.

At each dose, the Bayesian probability of an individual exceeding the Cmax threshold in Part 1 and the Bayesian probability of an individual exceeding the AUC threshold in Part 2 will be calculated and compared with 50%. This will be used to help selection of the next dose together with safety and tolerability data. The Bayesian probability will be based on Whitehead's model shown below [Whitehead, 2001] using non-informative prior for model parameters.

$$y_{ij} = \theta_1 + \theta_2 d_{ij} + s_i + \epsilon_{ij}$$

Where y_{ij} is log-PK of i -th participant to j -th dose, d_{ij} is j -th log-dose administered to i -th participant. θ_1 and θ_2 are population intercept and slope, respectively. s_i is random effect of i -th participant and ϵ_{ij} is random error of i -th participant in j -th dose.

When intra-participant variability cannot be estimated during PK predictions in Part 1 (i.e., early on in the study when there is not sufficient information to estimate intra-participant variability) and for conducting prediction of all doses in Part 2, the same Whitehead's model will be used for Bayesian probability calculations as below.

$$y_i = \theta_1 + \theta_2 d_i + \epsilon_i$$

Where y_i is log-PK of i -th participant, d_i is the log-dose administered to i -th participant. θ_1 and θ_2 are population intercept and slope, respectively and ϵ_i is random error of i -th participant.

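### The Part 1 dose-proportionality priors are labelled non-informative, but as written (a separate Gamma(0.01, 0.01) variance per participant) they are informative and can widen the slope's credible interval

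*SAP*

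**What the plan says.** SAP 8.1.5.1.1 fits a Bayesian power model to the Part 1 log-PK data, with an intercept, a slope on log-dose, a participant effect s_i and a residual. Of the slope, which is the dose-proportionality constant, it says: "The point estimate and 95% credible interval for this parameter will be estimated and reported".

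The priors follow under the label "Non-informative prior distributions for the estimated parameters are defined below". The intercept and slope each get N(0, 10²), and the participant effect gets N(0, τ_i). The line for τ_i reads "\tau_i \sim Gamma(0.01, 0.01" and the residual line reads "\sigma^2 \sim Gamma(0.01, 0.01" (closing brackets cut off here). The subscript i on τ appears in both places where τ is used.

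The section does not use the words precision, rate or scale. It plans no prior-sensitivity analysis. It also has no model-checking entry, although the accumulation, steady-state and relative-bioavailability sections that follow it each have one.

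**The concern.** The section writes its normal distributions with a variance as the second argument: N(0, 10²) for the regression parameters, and N(·, σ²) with the Gamma placed on σ². On that notation τ_i is a variance, and each participant has their own. No common between-participant variance is defined, so little is learned about between-participant spread by pooling over people.

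Gamma(0.01, 0.01) on a variance has most of its mass piled up next to zero. With two active doses per participant in Periods 1 to 3, the data can do little to move each τ_i away from its prior. If participant effects are under-fitted, their variation has to go into σ², and the slope loses part of the within-participant comparison that a crossover provides. What is at stake is the width of the reported interval for a secondary PK objective, and whether two programmers working from the same text would fit the same model.

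**Working it through.** **No figure to reproduce.** Neither document states an expected interval width or any operating characteristic for this slope.

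**Inputs from the documents.**
- Protocol 4.1: "In each escalating dose period, 6 participants will be randomized to receive VH3739937", and "each participant will receive placebo at least once". Under Table 7 each participant has two active doses and one placebo in Periods 1 to 3.
- Protocol 4.3.2 gives the doses: "SAD treatment Periods 10 mg, 30 mg, 80 mg, 160 mg, 320 mg and 640 mg". That makes 6 doses × 6 active = 36 active observations on 18 participants.
- Protocol 9.5 simulates with slope 1 and two variability cases: CVw/CVb 12.5/25 (low) and 50/50 (high).
- The documents disagree on who receives 800 mg. SAP 2.3 enrols new participants; Protocol 4.1 draws them from Cohorts 1 and 2. The check was run without 800 mg, with six new active participants, and with six existing ones.
- All other CV pairs below are assumptions, used to show the range.

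**Step 1: prior mass near zero.** For shape 0.01 and rate 0.01 and small x, P(τ_i < x) ≈ (0.01x)^0.01 / Γ(1.01), with Γ(1.01) = 0.9943.
- x = 10⁻¹⁰: 10^(−0.12) / 0.9943 = 0.763
- x = 10⁻⁶: 10^(−0.08) / 0.9943 = 0.837
- x = 0.0606, the log-scale variance for a 25% CV, since ln(1 + 0.25²) = 0.0606: (0.000606)^0.01 / 0.9943 = 0.934

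Reading 0.01 as a scale concentrates the mass further: P(τ_i < 10⁻¹⁰) = (10⁻⁸)^0.01 / 0.9943 = 0.837.

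**Step 2: where the variation goes.** At 12.5/25 the true residual SD is √ln(1 + 0.125²) ≈ 0.125. Under the priors as written its posterior mean is about 0.21. The excess variance is 0.21² − 0.0155 ≈ 0.029. Against a between-participant variance of 0.0606 that is 0.029 / 0.0606 ≈ 0.47, so roughly half of the between-participant variance has moved into the residual.

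**Step 3: interval width.** Trials were simulated at slope 1 (60 to 80 per scenario) and fitted by Gibbs sampling. Direct numerical integration in 12 trials for each of five scenarios gave closely similar width ratios. The entries are median ratios of 95% interval width, ranging over the designs run. The first comparator is one common variance with a half-normal(0, 1) prior on the SD. The second is one common variance with the same Gamma prior.

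| CVw/CVb (%) | As written ÷ common, half-normal SD | As written ÷ common, same Gamma |
|---|---|---|
| 12.5/25 (protocol low) | 1.48–1.63 | 1.43–1.60 |
| 50/50 (protocol high) | 1.10–1.18 | 1.00–1.04 |
| 25/25 | 1.10–1.17 | 1.00–1.04 |
| 25/35 | 1.24–1.30 | 1.11–1.20 (800 mg designs) |
| 25/50 | 1.45–1.61 | 1.40–1.54 |
| 50/25 | 1.01–1.04 | not reported |
| 12.5/50 | 2.35–2.72 | 2.71 (no 800 mg) |

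REML intervals, computed for the two 800 mg designs, gave nearly the same ratios as the half-normal comparator. Single trials vary: with new participants at 800 mg, the 10th to 90th percentiles are 1.24–1.82 at 12.5/25 and 1.02–1.28 at 50/50.

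In absolute terms, for that same design, the mean width is 0.104 against 0.068 at 12.5/25, about ±0.052 against ±0.034. At 50/50 it is 0.268 against 0.233, about ±0.134 against ±0.117.

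**Step 4: two causes.** The second ratio column isolates the participant index. It is large where CVb is about twice CVw or more, and close to 1 at 25/25 and 50/50. In those two cases the widening comes almost wholly from putting the Gamma on a variance.

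**Step 5: the other reading.** If the same Gamma is placed on participant-level precisions, the ratio to the half-normal comparator is 0.97–1.07, so there is essentially no widening.

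**The case against.** The strongest reply is that Gamma(0.01, 0.01) is commonly a prior for precisions, and that this section's notation is loose enough not to bear a literal reading. For example, it describes a normal distribution centred on the observed log-PK value as the posterior of the mean. If precisions were intended, the widening vanishes even with the participant index left in. This stands as a limit on the size of the effect. It does not rescue the text, which puts the Gamma explicitly on σ² and nowhere mentions a precision.

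It is also fair to say that dose proportionality is a secondary objective, that Protocol 9.1 tests no hypotheses, that no acceptance limits for the slope are set, and that the error is conservative: coverage was not reduced in the simulations. All of this stands.

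Three stronger readings are tempting, and none is supported.
- A reader might take the widening as one fixed percentage. It depends on CVw, CVb, the comparator and the parameterisation.
- A reader might infer from the prior mass alone that most participant effects vanish. The posterior at 12.5/25 shows about half of the variance moving.
- A reader might extend the point to dose escalation, because SAP 3.1 speaks of "using non-informative prior for model parameters" for the same model form. That section specifies no Gamma and no τ_i, so nothing shows that these priors are used there.

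**Conclusion.** The non-informative label is wrong for the priors as written. On the SAP's own notation, and taking 0.01 as a rate, the interval for the Part 1 slope is too wide. The median widening is about 50–60% at the protocol's low-variability case and about 10–18% at its high-variability case, assuming slope 1 and the Table 7 design with or without 800 mg. The assumed cases outside the protocol run from almost none (50/25) to more than double the width (12.5/50). If precisions were meant, the effect is essentially nil and the defect is one of specification only.

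The consequence is lost precision in a secondary estimate. The documents do not support a claim of under-coverage or of harm to a primary endpoint. The correction is worth making because it is cheap and because the section plans no check that would expose the problem.

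**What to change.** In SAP 8.1.5.1.1:
- Define one common between-participant variance, s_i ~ N(0, τ²).
- Put Gamma(0.01, 0.01) on the precisions 1/τ² and 1/σ², or use a weakly informative prior on the two SDs. The half-normal used above is one option, not a requirement.
- State whether each parameter is a variance or a precision, and whether the second Gamma argument is a rate or a scale.
- Add a short prior-sensitivity check, for example a refit under one alternative prior with both intervals reported.

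The cost is a few lines of SAP text and of model code. No data collection or design feature changes.
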